3.4 Primary Safety Endpoints

Patients will follow-up after the first injection at 4-weeks, 8-weeks, 12-weeks, and 6 months post injection. During follow-up appointments patients in this study will be monitored based on history and physical exam for any side-effects associated with the administration of local soft tissue injections of dexamethasone or ketorolac.

Patients can withdraw from the study at any time if they wish. Patients whose symptoms do not improve and are candidates for surgery can withdraw from the study and have surgery to correct their specific pathology (secondary endpoint). Patients enrolled in the study will be counseled regarding the likelihood of

the injections working and will be given the opportunity for a second injection at 4 weeks from the time of the first injection if no significant symptoms have resolved. Ultimately it will be up to the patient whether they chose another injection or if they want to resort to a surgical intervention.

Patients who receive ketorolac by randomization as the therapeutic option will have an expected failure rate of approximately 30-50% based on clinical experience and literature review that shows the failure rate of dexamethasone (standard of care) on trigger fingers. The study population will be statistically analyzed biannually to determine if there is a significant difference in the rate of failures between the two groups, however a sizeable study population needs to be established before these conclusions can be drawn. If the rate of failure proves to be statistically significant between the ketorolac and dexamethasone group then the study will have to be ethically abandoned. This determination needs to take into consideration the pretreatment symptoms of the patient since patients who begin treatment with a severe trigger finger (quinnell score=4) have a different prognosis compared to patients who begin with a mild trigger finger (quinnell score=1).

4 Subject Selection and Withdrawal

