7.1 Sample Size Determination

The sample size as stated above was derived by a power analysis. A power analysis indicated that a total sample size of 200 patients randomized equally (1:1 randomization) to each treatment arm (i.e trigger finger, De Quervain's disease, and tennis elbow) without any blocking or stratification would provide 80% statistical power (alpha=.05, beta=0.20) to detect a 10% difference in mean DASH scores between cohorts assuming a common standard deviation of 25% (effect size = 10/25 = 0.4). To account for an estimated 30% loss to follow-up, we plan to enroll a total of 260 patients per treatment arm (i.e. trigger finger, De Quervain's disease, and tennis elbow). In total, there will be approximately 780 patients enrolled among all treatment arms, however we expect the trigger finger group to be the treatment arm that most rapidly enrolls patients.

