9.4 Study Electronic Data

Data will be maintained on a database on a computer which the investigators of this study as well as research assistants have access (however not everyone will see the data due to blinding of the physicians involved in the study). The data will be kept on an NYU research network drive that is password protected. If the data is shared among the investigators it will also be emailed within the NYU email system which is also password protected and encrypted.

All data will be stored for future use. It will take approximately 1-2 years to obtain the number of patients required for the trigger finger arm of the study due to the multitude of patients requiring trigger finger injections in everyday practice. However, it can take longer for the other arms of the study to collect the required amount of patients. The following list explains how this long term data will be handled:

 Data will contain patient names abbreviated with initials of first and last names as well as medical record numbers attached in order to easily obtain more information on the patient in the hospital electronic medical record (EMR)

- Data will be stored indefinitely until it is determined that enough data has been obtained to publish results.
- Data will be kept on an NYU research network drive that the department of hand surgery maintains and is password protected. The resident investigator of this study along with hand department research assistants will have access to the data however any physicians involved in the treatment of these patients will not be able to see the data for blinding purposes.
- Data stored for future use will continue to be maintained in the event a retrospective review of the data is conducted (pending an IRB approval for this as well). At this time it is unknown what this data can also be used for aside from the primary purpose of the study.
- Once the study is complete the results will be shared among physicians. A subject's research
 data will be provided to subjects upon request. Patient will only be told their personal data
 outcomes and the general outcomes of the study as a whole however other patient information
 will be kept from them as per patient confidentiality rules.
- Storage for future use is not optional. This data needs to be stored because it can be used for other research in the future (retrospective reviews, etc).

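### Section 3.4 makes one study-wide failure comparison and has one action, abandoning the whole study, although each diagnosis has its own endpoints and sample size and trigger finger is expected to fill first

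*Combined protocol and SAP*

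**What the plan says.** Section 3.4 sets the rule in three steps, none of which mentions diagnosis:

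- Who is analysed: "The study population will be statistically analyzed biannually".
- What is compared: whether there is a "significant difference in the rate of failures between the two groups".
- What follows: if the rate differs significantly "between the ketorolac and dexamethasone group then the study will have to be ethically abandoned".

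Two qualifications are attached. One concerns size, without a number: "however a sizeable study population needs to be established before these conclusions can be drawn". The other concerns prognosis: "This determination needs to take into consideration the pretreatment symptoms of the patient". Its only example is the Quinnell score, which applies to trigger finger alone. The anticipated failure rate of 30-50% also comes from that disease, through clinical experience and a "literature review that shows the failure rate of dexamethasone (standard of care) on trigger fingers".

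Elsewhere the diagnoses are handled one by one. Section 3.2 makes the primary endpoint depend on the diagnosis and lists different examination signs for each. Section 7.1 sizes each diagnosis at 200 evaluable and 260 enrolled, and adds that "we expect the trigger finger group to be the treatment arm that most rapidly enrolls patients". Section 9.4 expects the trigger finger arm to take 1-2 years and says that "it can take longer for the other arms of the study to collect the required amount of patients".

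**The concern.** The unit that is monitored and closed (the study) is not the unit that is sized and given endpoints (the diagnosis). Two consequences follow while enrolment is uneven.

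- A difference that exists only in trigger finger can drive the study-wide comparison, because that disease supplies most of the early data. The only action available then closes De Quervain's and epicondylitis while they are part-enrolled, although nothing has been learned against ketorolac in either.
- A difference that exists only in a slower disease is averaged with trigger-finger patients who do not show it. It is seen later or less often, and patients with that disease go on being randomised.

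This is separate from the choice of significance boundary. A well-chosen boundary applied to the study as a whole would have the same two properties.

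**Working it through.** **Step 1. Is each diagnosis a self-contained comparison?** Section 7.1 gives a difference of 10, SD 25, power 80% and alpha 0.05 (taken as two-sided). Patients per drug = 2 × (1.960 + 0.842)² × 25² / 10² = 98.1, rounded up to 99, or 198 in total. The t-test version gives 99.1 per drug, so 100 per drug and 200 in total. The protocol's 200 is reproduced, and it is the requirement for one two-drug comparison within one diagnosis. 3 × 260 = 780.

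**Step 2. Inputs for the illustration.** The documents give no interim counts by diagnosis, so these are assumed: 260 in trigger finger and 65 (25% of target) in each other disease, 1:1 allocation, and one look at two-sided 5%. Failure on dexamethasone is set at 40%, the middle of the range in 3.4. Pooled patients per drug = (260 + 65 + 65)/2 = 195.

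Power = Φ((d − z·s0)/s1) plus the small opposite tail, with s0 = √(2p̄(1−p̄)/n) and s1 = √((p1(1−p1) + p2(1−p2))/n). The pooled excess is the disease excess times that disease's share of patients.

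**Step 3. Excess of 20 points in trigger finger only.** Pooled ketorolac rate = 0.40 + 0.20 × 260/390 = 0.533. Power = Φ((0.1333 − 1.96 × 0.0505)/0.0501) = Φ(0.685) = 75%. If only 70% are evaluable (the loss assumed in 7.1), n = 136.5 per drug and power = Φ((0.1333 − 1.96 × 0.0604)/0.0599) = Φ(0.25) = 60%.

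**Step 4. Excess of 25 points in De Quervain's only.**

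| Test | Rates | n per drug | Detected |
|---|---|---|---|
| Pooled, 5% | 0.40 v 0.442 | 195 | 13% |
| Within disease, 5% | 0.40 v 0.65 | 32.5 | 52% |
| Within disease, 5%/3 | 0.40 v 0.65 | 32.5 | 35% |
| Pooled, 5%, slower diseases at 130 each | 0.40 v 0.4625 | 260 | 30% |
| Within disease, 5%, at 130 | 0.40 v 0.65 | 65 | 82% |

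The third row uses z = 2.394: Φ((0.25 − 2.394 × 0.1239)/0.1199) = Φ(−0.39) = 35%. With a 20-point excess the first two rows become 10% and 36%. Moving the dexamethasone rate between 30% and 50% leaves Step 3 at 75-78% and the first two rows at 13-14% and 52-55%.

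**Step 5. Repeated looks.** A simulation used six half-yearly looks, each at unadjusted 5%. Each diagnosis ended with 100 evaluable patients per drug; trigger finger filled in 1 to 2 years and the others in an assumed 3. A 20-point excess in trigger finger only stopped the whole study in 59-70% of runs. A 20-point excess in epicondylitis only was flagged in 44-47% by the pooled test and in 87% by a within-disease test. Both sets of tests are unadjusted, so part of this gap would close once alpha is controlled.

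**Step 6. What splitting the rule costs.** Three independent unadjusted tests give 1 − 0.95³ = 14% for at least one false closure at one look, against 5% pooled. Over the six looks of Step 5, with trigger finger full at 1.5 years, this is about 38% against 14%. For a 20-point excess common to all diseases on the Step 2 counts, the pooled test detects 98%, a trigger-finger test 90%, and a test within a slower disease 36%.

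**The case against.** Section 3.4 never says that failures are pooled across diagnoses. It names no test, no definition of failure and no minimum size, and its failure rate and its prognostic example both come from trigger finger, so it may have been written with that disease in mind. Sections 8.4 and 10.1 point to a Data and Safety Monitoring Plan that is not among the documents and could state the unit. This limits the claim to what 3.4 says at face value. It does not remove it: population, comparison and action are all study-wide there, and a cure in an unseen document cannot be assumed.

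A reader might infer that these are three separate trials. The documents do not support that. There is one objective, the quickDASH, EQ-5D and pain scales are shared, randomisation is unstratified, and under 5.5 a patient's drug is carried over to further sites. The diagnoses therefore share patients and allocations.

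A reader might also infer that an excess in a slower disease would be hidden. Step 5 shows dilution: the pooled test still flags it in about 45% of runs.

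Finally, stopping everything on an off-label agent because of one disease can be defended as caution, and replacing the pooled test by three unadjusted ones would be worse on false closures and on an excess common to all diseases (Step 6). That stands, and it shapes the remedy. The instruction to weigh pretreatment symptoms is not an answer, because it concerns severity and does not name diagnosis.

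**Conclusion.** The concern holds as a mismatch between the monitoring rule in 3.4 and the by-diagnosis design in 3.2 and 7.1, and it should be corrected. Its direction follows from the text and from uneven enrolment. Its size rests on assumed interim counts, assumed excesses and a failure rate that the protocol takes from trigger finger.

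On those assumptions, a difference confined to trigger finger closes two unanswered comparisons with a probability of roughly 60-75% at a single look. A large excess confined to one slower disease is detected at one look with a probability of 13% pooled, against 35-52% within the disease. Over six unadjusted looks, a 20-point excess in one slower disease is flagged about 45% of the time pooled against 87% within it. The documents do not support saying that the protocol prescribes a specific pooled test, or that such an excess would go unseen.

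**What to change.** Reword 3.4 as follows.

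- At each look, report failures within each diagnosis (trigger finger stratified by baseline Quinnell grade) and a pooled comparison stratified by diagnosis.
- Let a by-diagnosis finding govern enrolment in that diagnosis only. Keep the stratified pooled comparison as the trigger for study-wide action.
- State in advance how a pooled result that comes from one diagnosis is told apart from one shared by all, for instance by the pooled estimate with that diagnosis left out. Without this, the Step 3 scenario would still cross a 2.5% pooled test about 66% of the time: Φ((0.1333 − 2.241 × 0.0505)/0.0501) = Φ(0.40).
- Share one overall alpha across these tests and across looks.
- State how the rule applies to patients whose drug is carried over to further sites under 5.5.
- Reconcile 3.4 with the Data and Safety Monitoring Plan.

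The cost is protocol wording, a few extra tables per look, and somewhat lower power for each test. If half the alpha is kept for the pooled comparison, detection of a common 20-point excess at one look is 96% instead of 98%: Φ((0.20 − 2.241 × 0.0506)/0.0496) = Φ(1.74). Dividing the other half by three lowers the within-disease figure for the 25-point De Quervain's excess to 26%: Φ((0.25 − 2.638 × 0.1239)/0.1199) = Φ(−0.64). That is still twice the 13% of the present rule. No extra patients, visits or data are needed.

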3.2 Primary Study Endpoints

The primary endpoint will be functional outcome scores at various follow-up time points using the quickDASH and EQ-5D questionnaire as well as a pain visual analog scale. The primary endpoint for the study would be resolution of symptoms or surgical intervention.

Primary endpoints will depend on the diagnosis of the patient. The following details what will be assessed at each follow-up visit after the initial injection:

- 1) Trigger finger group primary endpoint measures include the resolution of objective triggering and resolution of tenderness at the A1 pulley at subsequent follow-up visits. In addition, patients will be graded based on the Quinnell system to monitor for improvement: 0-normal movement of finger; 1-uneven movement; 2-active correctible locking of digit; 3-passively correctible locking; 4-fixed deformity (15). Patients will complete the quickDASH and EQ-5D questionnaires as well as a pain visual analog scale at each follow-up visit (27).
- 2) De Quervain's tenosynovitis group primary endpoint measures will include objective physical exam findings for the resolution of pain/tenderness over the 1st dorsal extensor compartment and the resolution of pain elicited during the Finkelstein test. In addition, patients will complete the quickDASH and EQ-5D questionnaires as well as a pain visual analog scale at each follow-up visit.
- 3) Lateral epicondylitis of the elbow group primary endpoint measures include the resolution of lateral elbow pain/tenderness over the extensor origin and the resolution of pain at the lateral epicondyle with resisted wrist extension during follow-up examinations. Patient grip strength will also be measured in this cohort using a hand dynamometer. Grip strength will be measured at each follow-up and the average of three tests with 20 second rests in between will be recorded. The contralateral side will also be measured for comparison. Lastly, patients will complete the quickDASH and EQ-5D questionnaires as well as a pain visual analog scale at each follow-up visit.

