4.1 Inclusion Criteria

- Patients must be diagnosed with at least one of the following: trigger finger, de quervain's tenosynovitis, or tennis elbow (lateral epicondylitis)
- Subjects may be treated for multiple sites of pathology simultaneously or sequentially and up to three sites of pathology can receive an injection during an office visit
- Subjects may have a maximum total of two injections at each site of pathology during the study
- Age 18 years of age or older from all racial/ethnic types
- · Both males and females
- Study participants will not receive splinting as a therapeutic addition to their treatment.
- Study participants will include any NYU employee or students as these individuals also can get hand and upper extremity pathology. It will be specifically reiterated to them that their academic status or grades, or employment will not be affected by their decision to participate in this study. Record of the participation cannot be linked to an academic record.

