5.8 Blinding of Study Drug

The study will be a double-blinded prospective randomized controlled trial. Drugs will be stored in the local clinic/office medication storage room. When a patient is enrolled and consented into the study a random envelop (labeled with an identification number) will be opened and in it will contain the group that the patient is randomized to: steroid or ketorolac. On the date of the planned injection a nurse, resident, fellow or research assistant present at the site and not directly involved in the patient's care will draw up the medication and hand it to the physician who will administer the drug. Both the patient and the treating physician are blinded to the identity of the medication. Patient data will be recorded and kept in the envelope and only the hand department research assistant or the resident in charge of this project (who will not be directly involved in patient care) will know the identity of the treatment given to the enrolled patients. Because both liquids are clear the contents of the syringes do not need to be covered

6 Study Procedures

A specific patient population with hand and upper extremity pathologies will be studied including trigger finger, De Quervain's tenosynovitis, and lateral elbow epicondylitis. Patients with trigger finger will be diagnosed clinically by observing symptoms of catching or triggering of the digit with range of motion and tenderness localized to the A1 pulley. Patients with De Quervain's tenosynovitis will be identified clinically as having pain/tenderness at the first dorsal extensor compartment combined with a positive Finkelstein test (pain during full thumb adduction with ulnar deviation of the wrist). Patients with tennis elbow (lateral epicondylitis) will be defined as having lateral elbow pain/tenderness over the extensor origin and/or pain at the lateral epicondyle with resisted wrist extension.

Patients will be consented at the time of their visit with the hand surgeon. Based on inclusion/exclusion criteria it will be determined whether or not to enroll the patient in the study. Consent will be performed by discussing the study with the patient in the privacy of the exam room and having them sign the written consent form that will be IRB approved. There is no payment to the patient for participation and they will be charged for their normal office visit for treatment rendered.

7 Statistical Plan

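### Section 3.4 requires trigger-finger severity in a decision that can end the trial, but no pre-injection grade is scheduled and no adjustment is specified

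*Combined protocol and SAP*

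**What the plan says.** - **Section 3.4** plans a statistical comparison of failure rates twice a year and says the study must stop if the difference is significant. The decision has to allow for the patient's symptoms before treatment, because "patients who begin treatment with a severe trigger finger (quinnell score=4) have a different prognosis" from those who begin at grade 1. No method is given. Conclusions are to wait until the study population is sizeable.
- **Section 3.2** defines the scale as "0-normal movement of finger; 1-uneven movement; 2-active correctible locking of digit; 3-passively correctible locking; 4-fixed deformity". The list that contains it opens with "The following details what will be assessed at each follow-up visit after the initial injection".
- **Section 5.5** describes envelopes generated by software that picks one of the two drugs at random. **Section 7.1** sizes the trial "without any blocking or stratification".
- **Section 7.2** compares quickDASH and EQ-5D, and their changes from baseline. Examination findings and symptom resolution are secondary. It names no covariate or stratum.
- **Section 6** diagnoses trigger finger by "observing symptoms of catching or triggering of the digit with range of motion and tenderness localized to the A1 pulley". Section 4.1 asks only for the diagnosis and sets no range of grades.
- **Sections 4.1 and 5.5** let one patient contribute several sites, all given the same drug.

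**The concern.** The protocol identifies a prognostic factor and makes it a condition of its most consequential decision, but does not supply what is needed to apply it. A baseline value is presumed and not scheduled, and nothing says how it should enter the comparison. Whoever carries out a biannual look would have to choose how to weigh severity with the failure counts already in view. At the final analysis, the comparisons of failure, resolution and quickDASH would forgo whatever precision the grade could add.

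A second, smaller matter is that the entry definition and the population described in section 3.4 do not clearly agree at the severe end of the scale.

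**Working it through.** **1. The plan's own figure.** Section 7.1 gives a difference of 10, SD 25, alpha 0.05 and power 80%. Taking alpha as two-sided:

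n per drug = 2 × (1.960 + 0.842)² × (25/10)² = 2 × 7.85 × 6.25 = 98.1, so 99 per drug and 198 in total.

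The t-test version needs 99.08, so 100 per drug and 200 in total, as stated. (One-sided alpha gives 156 and does not match.) The figure contains no term for a covariate or stratum, so severity plays no part in the sizing. Nothing in this point makes the 200 wrong.

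**2. What section 3.4 needs, against what is provided.**

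| Needed | Provided |
|---|---|
| A grade before the first injection | 3.2 lists grading for follow-up visits; a baseline grade is only implied |
| Balance by design, or | None (5.5, 7.1) |
| Adjustment in the analysis | None named in 7.2; no method in 3.4 |

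**3. Size for the failure comparison.** The documents give neither the mix of grades nor failure by grade. Assumptions: share of digits at grade 4, p = 0.20; failure at grade 4 higher than in the rest by g = 0.20 to 0.40; overall failure f = 0.40, the middle of the 30–50% in section 3.4; digits independent. The implied rates are 56% v 36% for g = 0.20 and 72% v 32% for g = 0.40.

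- Share of variance due to grade = p(1−p)g² / [f(1−f)].
- g = 0.20: 0.16 × 0.04 / 0.24 = 2.7%. g = 0.40: 0.16 × 0.16 / 0.24 = 10.7%.
- Reduction in standard error = 1 − √(1 − share): 1 − √0.973 = 1.3%, and 1 − √0.893 = 5.5%.
- With f = 0.30 the shares are 0.0064/0.21 = 3.0% and 0.0256/0.21 = 12.2%. With f = 0.50 they are 0.0064/0.25 = 2.6% and 0.0256/0.25 = 10.2%. The answer hardly moves.

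The same result in percentage points, with SD of imbalance = √(2 × 0.2 × 0.8 / n), grade's part = 1.96 × g × that SD, and full sampling range = 1.96 × √(2 × 0.24 / n):

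| n per drug | SD of imbalance in grade 4 | 95% range from grade | Full 95% sampling range |
|---|---|---|---|
| 25 | 11.3 | ±4.4 to ±8.9 | ±27.2 |
| 50 | 8.0 | ±3.1 to ±6.3 | ±19.2 |
| 100 | 5.7 | ±2.2 to ±4.4 | ±13.6 |

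The third column is a component of the fourth, not an addition to it. These figures are on the risk-difference scale.

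**4. Size for quickDASH.** The documents do not say how strongly grade relates to quickDASH. If it explained 5%, 10%, 20% or 30% of the outcome variance, replacing the SD by 25 × √(1 − R²) would cut the required 198 to 188, 178, 158 or 138. Power at 100 per drug would be 83%, 85%, 88% or 92%, against 81% unadjusted. These values illustrate a range and are not a forecast.

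**5. Entry definition against the scale.** Grades 2 and 3 (locking that can be corrected) fit section 6. Grade 1 (uneven movement) may or may not count as catching. Grade 4 (fixed deformity), read literally, does not show triggering through a range of motion, yet section 3.4 speaks of patients who begin there.

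**The case against.** The strongest reply is that an unadjusted comparison in a randomised trial is valid. That stands. A reader might infer that chance imbalance in severity would create a false drug difference, especially at an early look. The documents do not support that: under simple randomisation this imbalance is already inside the standard error, the test keeps its nominal error rate, and section 3.4 itself holds back conclusions until numbers are sizeable.

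It can also be said that the plan partly deals with severity. Section 3.4 does ask for it in the failure decision, and section 7.2 analyses change from baseline, which uses baseline function. Both are true, but the first has no method and no scheduled grade behind it. The second uses quickDASH and EQ-5D, not Quinnell grade, and does nothing for failure.

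Three further readings go too far. Section 3.4 calls severity prognostic; it does not rank it as the strongest factor, and it does not link it to quickDASH. The documents do not show that the offices and the clinic will select different grades. And no grade is excluded by name, so section 6 cannot be said to bar grade 1 or grade 4. The tension is literal for grade 4 and arguable for grade 1.

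Finally, this concerns one of three disorders, and the assumed inputs are not the sponsor's. That limits the size of the point, but the gap between section 3.4 and section 7.2 remains.

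**Conclusion.** The point holds as a modest, worthwhile improvement. The plan requires pretreatment severity in a decision that can end the trial, but schedules no pre-injection Quinnell grade and specifies no way to use one. The consequences are an unspecified judgement at the biannual looks and some lost precision; there is no bias in the randomised comparison. Under the assumptions in step 3, the loss for the failure difference is about 3% to 11% of variance, or about 1% to 5.5% of its standard error. For quickDASH the gain depends on a correlation the documents do not give. The stronger reason to act is the first consequence: a rule set in advance is better than one chosen during a stopping decision.

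**What to change.** 1. **Sections 3.2 and 6:** record the Quinnell grade of each trigger digit before the first injection, preferably before the envelope is opened.
2. **Sections 3.4 and 7.2:** prespecify that grade as a covariate in the trigger-finger comparisons of failure and symptom resolution, including every biannual look, and alongside baseline quickDASH in the quickDASH model. State its coding in advance; the documents give no basis for a particular cut between grades. Report failure as a difference in risk, the scale used in step 3.
3. **Method:** digits of one patient share a drug and are not independent, so a plain Mantel-Haenszel test on digits would not be valid. Use, for example, a regression with patient-clustered standard errors, or one index digit per patient.
4. **Sections 3.2, 3.4 and 6:** reconcile the entry definition with the grade 4 patients that section 3.4 expects. Which grades are eligible is for the sponsor to decide.

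Items 1 to 3 cost one baseline entry on a scale already in use and slightly more analysis. They need no extra patients or visits and no change to the envelopes. Item 4 is a wording change unless the sponsor's decision alters who is eligible.
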